4.1 Inclusion Criteria

Subjects must meet ALL of the following inclusion criteria in order to be eligible for this study:

1. Male or female ≥ 18 years of age
2. Subjects with hyperlipidemia with LDL-C level >3.37 mmol/L (130 mg/dL) in fasting conditions at screening, treated with a stable dose of statin for at least 6 weeks or not treated with a statin at the time of informed consent.
3. Subjects willing to maintain stable standard cholesterol lowering diet (Appendix 1) and physical activity level throughout the study
4. Female of childbearing potential must have a negative urine pregnancy test at screening and randomization baseline Visit 2

Women are considered not of childbearing potential if they:

- a. Have had a hysterectomy, a bilateral oophorectomy or tubal ligation prior to Baseline Visit.
- b. Are postmenopausal defined as no menses for at least 1 year and have a serum FSH level of 40 IU/L.

Women of childbearing potential must agree to use an effective method of birth control throughout the study. Acceptable means of birth control include: implantable contraceptives, injectable contraceptives, oral contraceptives, transdermal contraceptives, intrauterine devices, male or female condoms with spermicide, abstinence, or a sterile sexual partner

5. Ability and willingness to give written informed consent and to comply with the requirements of the study

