6 STATISTICAL METHODOLOGY

6.1 Determination of Sample Size

Sample size computation was based on the change in LDL-cholesterol. Based on previous literature, we are expecting a mean decrease from baseline to follow-up in LDL-C of -0.30 mmol/L (11.6 mg/dl) in the placebo group and we are aiming to show that the addition of beta-glucan, either at 1.5 g, 3 g or 6 g, will further reduce LDL-C by -0.30 mmol/L, leading to an expected difference in change in LDL-C of 0.30

mmol/L between the placebo group and at least one of the active groups. The expected standard deviation of the change in LDL-C is 0.50 mmol/L (19.3 mg/dl). To reach a power of 80% in detecting this 0.30 mmol/L difference with a two-tailed significance level of 0.0167 (to account for three main comparisons (placebo vs. beta-glucan 1.5 g, placebo vs. beta-glucan 3 g and placebo vs. beta-glucan 6 g), 60 subjects per group were needed for a total of 240 subjects. To account for approximately 9% lost to follow-up, 264 subjects (66 subjects per treatment group) were randomized.

Sample size was calculated with nQuery + nTerim 2.0.

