6.4.1 Primary Analysis

The primary endpoint is the change from Week 0 to Week 12 in direct-measured LDL-C. The changes, as well as the LDL-C values at each study visit, will be summarized with descriptive statistics.

The primary endpoint will be compared between treatment groups using a repeated measures analysis of covariance (ANCOVA) model.. More specifically, the dependent variable will be the change from Week 0 in LDL-C (change calculated as post Week 0 level – Week 0 level) the model will include treatment group, time (Week 6 and Week 12) and treatment group x time interaction as well as the covariates of Week 0 value of LDL-C and Week 0 value of LDL-C x time interaction. An unstructured covariance structure will be

used to model the within-patient errors and the Kenward-Roger approximation will be used to estimate denominator degrees of freedom. Contrasts under this model will allow for the three main comparisons: placebo vs. beta-glucan 1.5 g, placebo vs. beta-glucan 3 g and placebo vs. beta-glucan 6 g. More specifically, the following hypotheses will be tested:

$$H_0: \Delta_{W12,\text{placebo}} = \Delta_{W12,1.5g} \quad \text{vs.} \quad H_1: \Delta_{W12,\text{placebo}} \neq \Delta_{W12,1.5g}$$

$$H_0: \Delta_{W12,\text{placebo}} = \Delta_{W12,3g} \quad \text{vs.} \quad H_1: \Delta_{W12,\text{placebo}} \neq \Delta_{W12,3g}$$

$$H_0: \Delta_{W12,\text{placebo}} = \Delta_{W12,6g} \quad \text{vs.} \quad H_1: \Delta_{W12,\text{placebo}} \neq \Delta_{W12,6g}$$

where $\Delta_{W12,\text{placebo}}$, $\Delta_{W12,1.5g}$, $\Delta_{W12,3g}$ and $\Delta_{W12,6g}$ are respectively the mean change from Week 0 to Week 12 in LDL-C in the placebo, beta-glucan 1.5 g, beta-glucan 3 g and beta-glucan 6 g group.

All sets of hypotheses will be tested at the 0.0167 significance level to maintain the overall type I error to 0.05 for the primary endpoint. These tests will be considered as the primary analysis of the study.

For illustrative purposes, changes within groups will be tested at the 0.05 significance level. Estimates of the changes within groups and of the between-group differences will also be presented along with 95% confidence intervals.

The same ANCOVA model will also allow for the examination of the change from Week 0 to Week 6 in LDL-C. In other words, the hypotheses described above will also be tested at Week 6 at the 0.05 significance level for illustrative purposes.

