9 APPENDICES

9.1 Appendix 1 - Schedule of visits

| Procedure/Visit | Screening Period (V1) | Randomization Baseline Visit (V2) | Visit 3 (V3) | End of Treatment Visit (V4) | Safety Follow-up Visit (V5) (telephone) |
|---|--------------------------|---|----------------------|-----------------------------------|--|
| | Week -1 Up to 7 days | Week 0 | Week 6 (± 5 days) | Week 12 (± 5 days) | Week 14 (± 5 days) |
| Informed consent form | X | | | | |
| Inclusion & Exclusion criteria | X | X | | | |
| Medical History | X | X | | | |
| Demographics | X | | | | |
| Physical examination | X | | | X | |
| Vital signs (blood pressure, pulse) | X | X | X | X | |
| Height | X | | | | |
| Weight | X | | | X | |
| Dietary counselling including alcohol consumption, and timing of statin vs. IP intake | X | X | X | | |
| Check compliance on statin and IP | | | X | X | |
| 12-Lead ECG | X | | | X | |
| Hematology | X | X | X | X | |
| AST, ALT, Creatinine | X | X | X | X | |
| Bilirubin | X | | | | |
| LDH, CPK | | X | X | X | |
| TG, TC, LDL-C, HDL-C | X | X | X | X | |
| LDL-C (direct-measured), VLDL-C, apo-B, Lp(a), non-HDL-C, small low-density lipoprotein (LDL) subclass particle concentration | | X | X | X | |
| HbA1c, Insulin, Glucose and hsCRP | | X | | X | |
| Concomitant medication | X | X | X | X | |
| Pregnancy test* | X* | X* | | | |
| Randomization | | X | | | |
| IP dispensing | | X | X | | |
| Adverse Events | X** | X** | X** | X** | X** |

*Female patients of childbearing potential will have a urine pregnancy test performed at the screening visit and at randomization (visit 2)

**Serious Adverse Events (SAEs) are captured from the time of consent through to week 14 safety Follow up phone call. AEs are captured between the time of randomization up to the last dose IP taken.

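### The primary model leaves out the screening LDL-C that every eligible subject already has; adding it as a covariate is an optional, nearly free gain in precision

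*SAP*

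**What the plan says.** The covariates of the primary model (SAP 6.4.1) are the Week 0 LDL-C and its interaction with time: "as well as the covariates of Week 0 value of LDL-C and Week 0 value of LDL-C x time interaction". No screening value appears in this model or in those of SAP 6.4.2, 6.4.3 and 6.4.5.

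A screening value exists by design. Protocol 4.1 makes entry depend on "LDL-C level >3.37 mmol/L (130 mg/dL) in fasting conditions at screening". In the visit schedule (SAP Appendix 1, Protocol Appendix 2) the row "TG, TC, LDL-C, HDL-C" is marked at screening, Week 0, Week 6 and Week 12. SAP 5.6 includes the screening panel among the central laboratory data. Protocol 6.1 places screening up to 7 days before Week 0, or longer when a 30-day supplement washout is needed.

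Direct-measured LDL-C is scheduled from Week 0 only; the screening panel lists plain LDL-cholesterol. The one planned efficacy use of the screening value is in SAP 6.2.1, where it stands in for a missing baseline.

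The sample size (SAP 6.1, Protocol 10.6) uses the unadjusted SD of change, 0.50 mmol/L, and takes no credit for any covariate.

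**The concern.** A single Week 0 reading is a noisy measure of a subject's usual LDL-C. A second reading taken shortly before it normally says something more about that usual level, and so about the Week 12 value. Entered as its own covariate, it lowers the residual variance and narrows the interval for all three primary contrasts, using data that will already be in the database. It need not be on the same scale as the outcome or come from the same assay.

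What is at stake is precision, not validity. Narrower intervals would help most if the true effect is smaller than the planned 0.30 mmol/L, since the trial's purpose (Protocol section 1) is to find out which dose works.

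**Working it through.** **1. The plan's own figure.** Inputs from SAP 6.1: "To reach a power of 80% in detecting this 0.30 mmol/L difference", "with a two-tailed significance level of 0.0167", SD of change 0.50. Placebo is pooled over the three tiers (3 × 22 = 66), so each contrast is 1:1. The noncentrality at 60 per group is 0.30 / (0.50 × √(2/60)) = 3.286 on 118 df. Power is 80.3% at 60 per group and 79.5% at 59, so "60 subjects per group were needed for a total of 240 subjects" reproduces. With 9% loss, 60 / 0.91 = 65.9, which gives the 66 randomized per group.

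**2. Simple case: equal correlation ρ between all visits, no truncation.** With complete data, an unstructured covariance and covariates interacted with time, the Week 12 contrast behaves like a Week 12 ANCOVA. Holding the SD of change at 0.50:

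- residual SD, Week 0 only: 0.50 × √((1+ρ)/2)
- residual SD, Week 0 plus screening: 0.50 × √((1+2ρ)/(2(1+ρ)))
- variance ratio: (1+2ρ)/(1+ρ)²

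| ρ (assumed) | SD, Week 0 only | SD, plus screening | Variance cut | Power at 60 per group |
|---|---|---|---|---|
| 0.5 | 0.433 | 0.408 | 11% | 91.2% → 94.3% |
| 0.7 | 0.461 | 0.420 | 17% | 87.0% → 92.9% |
| 0.8 | 0.474 | 0.425 | 20% | 84.8% → 92.3% |

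This is optimistic: it ignores the entry threshold, a different assay, and short-term variation that screening and Week 0 share.

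**3. Allowing for those features.** Let S, W0 and W12 be the screening, Week 0 and Week 12 values. The within-subject variance per visit is 0.50²/2 = 0.125. Assumed ranges: population mean 3.5 or 4.0; between-subject SD 0.6 or 0.9 (variance B); extra screening-method error SD m = 0 or 0.25; a fraction f of the 0.125 shared by S and W0. Then Var(S) = B + 0.125 + m², Cov(S,W0) = B + 0.125f, the other covariances equal B, and Var(W0) = Var(W12) = B + 0.125.

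Truncation at S > 3.37 uses k = (3.37 − mean)/SD(S), λ = φ(k)/(1−Φ(k)) and δ = 1 + kλ − λ². Each covariance Cov(X,Y) is reduced by (1−δ) × Cov(X,S) × Cov(Y,S) / Var(S).

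Most favourable case (mean 4.0, B = 0.81, m = 0, f = 0):

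- k = −0.63/0.967 = −0.65, λ = 0.434, δ = 0.529. The reduction is 0.471 × 0.81²/0.935 = 0.331.
- Var(W0) = Var(W12) = 0.935 − 0.331 = 0.604. Cov(W0,W12) = 0.81 − 0.331 = 0.479.
- Residual variance, Week 0 only: 0.604 − 0.479²/0.604 = 0.224 (SD 0.473).
- With screening added, truncation drops out. With ρ = 0.81/0.935 = 0.866 it is 0.935 × (1 − 2ρ²/(1+ρ)) = 0.183 (SD 0.428).
- The cut is 18% and power goes from 85.0% to 91.9%.

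Ranges over the two means and two between-subject SDs, n = 60 per group:

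| Shared f | Method error m | Variance cut | Power, Week 0 only | Power, plus screening | Gain (points) |
|---|---|---|---|---|---|
| 0% | 0 | 11.8–18.3% | 85.0–88.8% | 91.9–92.7% | 3.8–7.0 |
| 0% | 0.25 | 8.5–13.9% | 84.8–88.4% | 90.2–91.3% | 2.9–5.4 |
| 50% | 0 | 6.4–9.4% | 83.8–86.9% | 87.6–89.3% | 2.3–3.9 |
| 50% | 0.25 | 3.8–5.9% | 83.7–86.8% | 86.2–88.2% | 1.4–2.4 |
| 80% | 0 | 2.8–3.9% | 83.4–86.3% | 85.0–87.3% | 1.1–1.6 |
| 80% | 0.25 | 1.1–1.6% | 83.4–86.2% | 84.1–86.6% | 0.4–0.7 |

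In evaluable subjects, the extremes are worth 240/(1 − 0.183) − 240 ≈ 54 and 240/(1 − 0.011) − 240 ≈ 3 out of 240.

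**4. The limit and the cost.** If screening predicts Week 12 only through Week 0, the gain is zero. At each visit the model would go from five mean parameters (four groups, one slope) to six. A useless covariate would inflate the contrast variance by roughly 1/(240 − 6) ≈ 0.4% on average.

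**The case against.** The strongest reply is that nothing is broken. The model is valid, it follows the protocol's choice of Week 0 as the covariate (Protocol 10.3.1), and under the assumptions above it already has 83 to 89% power against a planned 80%. That stands, and it is why the point is graded as optional.

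The second reply is that the size is not known. Deriving 0.125 from the SD of change treats 12-week variation as independent visit noise. If much of it is slow drift, two readings a week apart share it and the second adds little. That also stands: a reader might take the 4% cut seen with up to half the variance shared as a minimum, but at 80% shared with a noisier assay it is near 1%.

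Three further readings go beyond the documents:

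- *Screening is a replicate of Week 0.* It is not listed as direct-measured, and after an extended washout it may predate the stopping of lipid-modifying supplements. It is a correlated covariate, which is enough for this purpose.
- *Any pre-randomization covariate removes bias.* Randomization protects comparisons within a tier. Placebo is pooled over three tiers enrolled in sequence (SAP 2.1), and SAP 3.2 shows that the statin entry criterion changed. Screening LDL-C introduces no bias, but it does not make the pooled placebo concurrent.
- *The same gain applies to the other lipids.* No gain has been computed for them.

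**Conclusion.** The point holds as a missed efficiency gain in a valid model. A reader might infer that the primary analysis is wrong or underpowered; the documents do not support that, because the 60 per group reproduces at 80.3% power with no credit for any covariate.

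Apart from the small cost of two parameters, adding screening LDL-C can only help precision on average. The estimate is a 1 to 18% cut in residual variance and about 0.5 to 7 points of power. It rests on the planned SD of 0.50 and on assumed population, assay and shared-variance values that the documents do not give. The direction is secure except in the limiting case; the size is not. This is a free improvement, optional rather than a correction.

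**What to change.** Before unblinding, add screening LDL-C and screening LDL-C × time to the covariates in SAP 6.4.1. Keep change from Week 0 in direct-measured LDL-C as the outcome and Week 0 as the baseline.

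Add one handling rule. Where screening replaces a missing Week 0 value (SAP 6.2.1), the same number would otherwise enter the model twice; where screening is missing, PROC MIXED would drop the subject's records. In both cases the subject should be retained by a simple pre-specified rule that ignores treatment assignment, for example filling the missing pre-randomization covariate with its overall mean.

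The matching screening value may be added in the same way in SAP 6.4.2 and 6.4.3 for TC, HDL-C, TG (on the log scale) and non-HDL-C (screening TC minus HDL-C).

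The cost is two parameters in the primary model and one rule, with no new samples, visits or subjects. The gain may be small if the screening assay differs or the sample predates a washout.

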Sample size computation is based on the change in LDL-C. Based on previous literature, we are expecting a mean decrease from baseline to follow-up in LDL-C of 0.30 mmol/L (11.6 mg/dL) in the control group and we are aiming to show that the addition of beta-glucan, either at 1.5 g, 3 g or 6 g, will further reduce LDL-C by 0.30 mmol/L, leading to an expected difference in change in LDL-C of 0.30 mmol/L between the control group and at least one of the active groups. The expected standard deviation of the change in LDL-C is 0.50 mmol/L (19.3 mg/dL). To reach a power of 80% in detecting this 0.30 mmol/L difference with a two-tailed significance level of 0.0167 (to account for the three main comparisons: placebo vs. beta-glucan 1.5 g, placebo vs. beta-glucan 3 g and placebo vs. beta-glucan 6 g), 60 subjects per group are required for a total of 240 subjects. To account for approximately 9% lost to follow-up, 264 subjects (66 subjects per treatment group) will be randomized.

Efficacy:

The primary dataset for efficacy analyses will be the set of all randomized subjects (ITT Population).

For the primary, secondary and exploratory endpoints, the values at each study visit and the changes from Week 0 to follow-up visits (week 6 and week 12) will be summarized for each treatment group using descriptive statistics. The changes will be compared between treatment groups using repeated measures analysis of covariance (ANCOVA) models adjusting for the Week 0 value. Contrasts under these models will allow for the three main comparisons: placebo vs. beta-glucan 1.5 g, placebo vs. beta-glucan 3 g and placebo vs. beta-glucan 6 g. For the primary endpoint, these comparisons will be done at the 0.0167 significance level. The significance level will be set to 0.05 for all other analyses.

Safety:

The primary dataset for safety analyses will be the set of all randomized subjects who received at least one dose of investigational product (IP) (Safety Population).

Adverse events will be coded using the Medical Dictionary for Regulatory Affairs (MedDRA) coding dictionary. Treatment-emergent adverse events will be summarized for each treatment group.

Treatment-emergent adverse events will be defined as adverse events with a start date on or after the first dose of study product.

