The EFSA Panel assumes that the target population is the general population and that the claimed effects refer to the maintenance of normal blood LDL-C concentrations, increasing in satiety which leads to a reduction in energy intake, reduction of post-prandial glycaemic response and improvement of the digestive function.⁽¹⁰⁾

A systematic review of 16 studies conducted by Q. Hou *et al.* has shown that oat intake reduced the concentrations of TC and LDL-C. It is thought that the cholesterol-lowering effect might be due to beta-glucan binding with bile acids which leads to decreased cholesterol absorption, increased expression of hepatic LDL-C receptor, and increased faecal bile acid excretion. The effect of beta-glucan on HDL-C has varied in those studies.

Hou *et al.* have also demonstrated that oat intake has a moderately beneficial effect on glycaemic control and lipid profile in patients with type 2 diabetes. The beneficial effect on blood lipids and glycaemia have been found to be linked to the increased viscosity of the food bolus, delayed gastric emptying, lengthened intestinal transit time, slowed absorption of nutrients especially carbohydrates, and enhanced satiety. The authors have also shown that the effects on health depend on the dosage, chemical structure, molecular weight, solubility and viscosity of the oat. No evidence has been found linking oat consumption and allergic reactions or disease; however, the authors recommend using pure oats without wheat contamination in wheat hypersensitive patients.⁽¹⁴⁾

CEAPRO's beta-glucan is a high-medium molecular weight soluble fibre obtained by a Pressurized Gas eXpanded® (PGX) method, which is a novel drying technique for processing water-soluble biopolymers. The use of high-medium molecular weight beta-glucan, obtained by the PGX method, for 12 weeks may significantly reduce the level of LDL-C and contribute to reducing the cardiovascular disease risk.

This phase II trial is indicated in the context of substantial scientific evidence on the cholesterol lowering effect of beta-glucan, the existence of a beta-glucan monograph published by Health Canada and the need to better delineate the effective dosage of the new formulation of CEAPRO's beta-glucan^{(15), (16)}.

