10.2 General Statistical Approach

This is a randomized, parallel study with four treatment groups (placebo, beta-glucan 1.5 g, beta-glucan 3 g and beta-glucan 6 g). The statistical analysis will focus on the comparisons of the three active groups vs. placebo.

Descriptive statistics of all study variables will be presented overall and broken down by treatment group. Number of observations, mean, standard deviation, median, minimum and maximum will be presented for continuous variables. Count and proportion will be displayed for categorical variables.

Basic assumptions of the proposed analyses will be checked and data transformation or other analyses could be done if appropriate. For example, as some endpoints are likely to be skewed (ex. triglycerides, hsCRP), log-transformation might be used, in which case descriptive statistics would also include geometric means.

All statistical tests will be two-sided. Tests involving the comparisons of the active groups vs. placebo for the primary endpoint will be conducted at the 0.0167 significance level. All other tests will be considered secondary or exploratory and will be conducted at the 0.05 significance level.

A statistical analysis plan (SAP) will be written to fully describe the statistical analyses that will be done. The SAP will be finalized prior to database lock and unblinding.

Statistical analyses will be done using SAS version 9.4 or higher.

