10.3.1 Analysis of the Primary Efficacy Endpoint

The primary endpoint is the change from Week 0 to Week 12 in direct-measured LDL-C. The changes, as well as the LDL-C values at each study visit, will be summarized with descriptive statistics.

The primary endpoint will be compared between treatment groups using a repeated measures analysis of covariance (ANCOVA) model adjusting for the Week 0 value of LDL-C. More specifically, the dependent variable will be the change from Week 0 in LDL-C (change calculated as post Week 0 level – Week 0 level). The model will include treatment group, time (Week 6 and Week 12) and treatment group x time interaction as factors. Contrasts under this model will allow for the three main comparisons: placebo vs. beta-glucan 1.5 g, placebo vs. beta-glucan 3 g and placebo vs. beta-glucan 6 g. More specifically, the following hypotheses will be tested:

$H_0: \square_{W12,placebo} = \square_{W12,1.5g}$ vs. $H_1: \square_{W12,placebo} \neq \square_{W12,1.5g}$

$H_0: \square_{W12,placebo} = \square_{W12,3g}$ vs. $H_1: \square_{W12,placebo} \neq \square_{W12,3g}$

$H_0: \square_{W12,placebo} = \square_{W12,6g}$ vs. $H_1: \square_{W12,placebo} \neq \square_{W12,6g}$

where $\square_{W12,placebo}$, $\square_{W12,1.5g}$, $\square_{W12,3g}$ and $\square_{W12,6g}$ are respectively the mean change from Week 0 to Week 12 in LDL-C in the placebo, beta-glucan 1.5 g, beta-glucan 3 g and beta-glucan 6 g group.

All sets of hypotheses will be tested at the 0.0167 significance level to maintain the overall type I error to 0.05 for the primary endpoint. These tests will be considered as the primary analysis of the study.

For illustrative purposes, changes within groups will be tested at the 0.05 significance level. Estimates of the changes within groups and of the between-group differences will also be presented along with 95% confidence intervals.

The same ANCOVA model will also allow for the examination of the change from Week 0 to Week 6 in LDL-C. In other words, the hypotheses described above will also be tested at Week 6 at the 0.05 significance level.

Because the SAS procedure PROC MIXED will be used, subjects with missing data at a given study visit will not be excluded from the analysis.

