6.4.4.2 Dose-Response Analysis

In order to visualize the dose-response relationship, a regression model including linear and quadratic terms will be used to characterize the relationship between dose level (considered as a continuous variable) and the change from Week 0 to Week 12 in direct-measured LDL-C. More specifically, the model will be:

$$Y_j = \beta_0 + \beta_1 d_j + \beta_2 d_j^2 + \varepsilon_j$$

where Y_j is the change from Week 0 to Week 12 of the j^{th} patient, β_0 is the intercept, β_1 is the coefficient of the linear dose term, β_2 is the coefficient of the quadratic dose term, d_j is the dose level (0g, 1.5g, 3g, 6g) and ε_j is the error term. A test of the null hypothesis $H_0: \beta_2 = 0$ versus the alternative hypothesis $H_1: \beta_2 \neq 0$ will be performed at the 0.05 significance level. Non rejection of the null hypothesis will result in dropping the quadratic term from the model and concluding that a linear relationship provides a better fit. Otherwise, the quadratic term will be kept in the model. A plot of the predicted dose-response curve with 95% CIs will be provided to visualize the dose response relationship, along with the estimate of the coefficients β_1 and β_2 (if applicable) with associated 95% CI and p-values.

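### Optional improvement, not an error: Holm's step-down in place of three fixed 0.0167 tests keeps the 5% family-wise error and adds power for a second and third effective dose

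*SAP*

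**What the plan says.** The primary endpoint is the Week 0 to Week 12 change in direct-measured LDL-C. It is analysed by a repeated-measures ANCOVA with three contrasts, each dose against a single placebo group. SAP 6.4.1 sets the decision rule: "All sets of hypotheses will be tested at the 0.0167 significance level to maintain the overall type I error to 0.05". The protocol has the same rule in its synopsis ("For the primary endpoint, these comparisons will be done at the 0.0167 significance level") and in 10.3.1 ("All sets of hypotheses will be tested at the 0.0167 significance level"). Protocol 10.2 and SAP 6.2 repeat it. No step-down procedure is named anywhere.

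The sample-size sections (Protocol 10.6, SAP 6.1) use the same 0.0167. They aim at a 0.30 mmol/L difference for at least one active group.

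On intervals, SAP 6.4.1 says: "Estimates of the changes within groups and of the between-group differences will also be presented along with 95% confidence intervals". It does not say whether they are adjusted for the three comparisons.

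The protocol's rationale cites "the need to better delineate the effective dosage of the new formulation". The SAP adds a curve fit: "In order to visualize the dose-response relationship, a regression model including linear and quadratic terms will be used".

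**The concern.** If the purpose is to delineate the effective dosage, it matters whether a second and a third dose also beat placebo. Under the fixed rule, success at one dose brings no relief for the others. A dose with p = 0.02 fails even when the other two are clearly significant. Holm's procedure relaxes the threshold as doses are rejected and keeps the same 5% family-wise guarantee, so the fixed rule gives up power that needs no extra subjects to recover.

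The dose-response regression does not fill this gap. It describes the shape of the curve and does not test each dose against placebo. The same contrasts are tested elsewhere (Week 6, the two per-protocol analyses, the secondary endpoints), but all at 0.05 and none as the primary analysis.

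**Working it through.** **Inputs from the documents.** Difference 0.30 mmol/L, SD of change 0.50, two-sided 0.0167, power 80%, 60 evaluable per group, 9% loss (Protocol 10.6, SAP 6.1). Each tier has 66 active and 22 placebo subjects, so pooled placebo is 3 × 22 = 66 and the four groups are equal. No interim efficacy analysis.

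**Step 1: reproduce the plan's figure.** Normal approximation: n = 2(2.393 + 0.842)² × 0.50² / 0.30² = 58.1, so 59. The exact two-sample t calculation gives 60, with power 80.3%. Inflation: 60/0.91 = 65.9, so 66; 240/0.91 = 263.7, so 264. The stated sample size is correct.

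**Step 2: thresholds.** With four groups of 60 and a pooled variance on 236 df, the standard error of a contrast is 0.50 × √(2/60) = 0.0913 mmol/L.

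| Level | Critical t | Smallest significant difference (mmol/L) |
|---|---|---|
| 0.05/3 | 2.411 | 0.220 |
| 0.025 | 2.256 | 0.206 |
| 0.05 | 1.970 | 0.180 |

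The fixed rule keeps every dose on the first row. Holm moves to the second row after one rejection and to the third after two.

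**Step 3: why Holm keeps 5%.** If m doses are truly ineffective, the first of them that Holm reaches is tested at no more than 0.05/m. The chance of any false rejection is therefore at most m × 0.05/m = 0.05, whatever the correlation from the shared placebo. Holm also rejects every dose that fixed tests at 0.05/3 reject. The plan's rounded 0.0167 (3 × 0.0167 = 0.0501) makes no practical difference.

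**Step 4: simulation.** At least 1,000,000 trials per scenario; 60 per group, shared placebo, SD 0.50, effective doses at 0.30 mmol/L.

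| Scenario | Quantity | Fixed 0.0167 | Holm |
|---|---|---|---|
| Three effective | Power per dose | 80.9% | 87.2% |
| | All three shown | 62.6% | 77.9% |
| | At least one rejection | 95.3% | 95.3% |
| Two effective | Power per effective dose | 80.9% | 83.6% |
| | Both shown | 70.0% | 75.4% |
| | At least one rejection | 92.2% | 92.2% |
| | Family-wise error | 1.7% | 3.9% |
| One effective | Power for that dose | 80.9% | 81.0% |
| | At least one rejection | 81.9% | 81.9% |
| | Family-wise error | 3.1% | 4.2% |
| None effective | Family-wise error | 4.4% | 4.4% |

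**Step 5: sensitivity to assumptions.** The model adjusts for baseline ("as well as the covariates of Week 0 value of LDL-C and Week 0 value of LDL-C x time interaction"), so the residual SD may be below 0.50. The documents give no adjusted value. An assumed SD of 0.40 needs a baseline-change correlation of √(1 − (0.40/0.50)²) = 0.60. With three effective doses, power per dose is then 95.4% against 97.8%, and all three are shown in 89.1% against 95.5%. Holm's family-wise error reaches its highest value of the cases run there, 4.6%, with two effective doses. With assumed graded effects of 0.15/0.22/0.30 at SD 0.50, power by dose is 22/50/81% (fixed) and 33/57/82% (Holm).

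**Step 6: intervals.** A 95% interval excludes zero at 0.180 mmol/L, while the fixed test needs 0.220. With three effective doses at SD 0.50, 24.5% of trials have at least one dose that fails at 0.0167 although its 95% interval excludes zero. Under Holm this is 7.3%. Holm brings the opposite mismatch: a rejected dose whose 98.33% interval includes zero occurs in 17.2%, 7.6% and 1.5% of trials with three, two and one effective doses.

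**The case against.** **Bonferroni is a legitimate choice, and Holm does nothing for the plan's own target.** Both parts stand. The sample size aims at a difference for at least one dose, and that chance is identical under the two rules. The largest gain needs 0.30 mmol/L at all three doses over a four-fold dose range, which the documents do not predict. Bonferroni also has simple matching intervals, and Holm does not.

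**Error control depends on the tiered design.** Doses are allocated in successive sets of 88, yet placebo is analysed as one group, so two-thirds of each dose's placebo comparators come from other tiers. A reader might infer that Holm secures 5% whatever happens over time. It does not; it needs each contrast to be valid. With an assumed drift of 0.05 mmol/L per tier (not in the documents), family-wise error with no effective dose is about 7.8% under both rules. With 3 g and 6 g effective it is 3.4% fixed against 6.7% Holm. Holm does not cause such a bias, but its later, looser steps pass more of it on.

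**The interval label is reporting style.** Largely true. SAP 6.4.1 names the 0.0167 tests as the primary analysis, so what counts as success is clear. A reader might infer that the 95% intervals are a flaw in the analysis; the text does not support that.

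**The change comes late.** SAP 6.1 already speaks of 264 subjects as randomized. That limits when the change can be made but does not rule it out, since "The SAP will be finalized prior to database lock and unblinding".

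**Conclusion.** The point holds as an optional, low-severity improvement. A reader might infer that the primary analysis is invalid or underpowered. It is neither: the fixed rule controls family-wise error at about 4.4% with the shared placebo when no dose works, and it delivers the stated 80% power.

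Holm's benefit is confined to trials in which two or more doses work. At SD 0.50 it adds about 6 points per dose and 15 points for showing all three when all have the planned effect, and about 5 points for showing both when two do. It adds 0.1 point when one works and nothing to the chance of at least one success. Its family-wise error was 3.9 to 4.6% in the cases run.

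These figures assume 60 evaluable per group, normal changes with a common SD, and no calendar-time effect across tiers. Holm does not remedy any bias from pooling placebo across tiers; that is a separate matter.

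**What to change.** Before database lock and unblinding:

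1. In SAP 6.4.1, replace the fixed-level sentence with wording such as: *The three Week 12 contrasts will be tested by Holm's procedure at an overall two-sided level of 0.05. The smallest p-value is compared with 0.05/3, the next with 0.025 and the largest with 0.05, stopping at the first non-significant result.*
2. As a minor accompaniment, add: *The 95% intervals for between-group differences are not adjusted for multiplicity.* This helps under either rule.
3. Align the level stated in SAP 6.2. SAP section 1 lets the SAP supersede the protocol. If the protocol synopsis, 10.2 and 10.3.1 are aligned as well, the amendment may need ethics review under Protocol 15.

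The sample-size text can stay, because Holm's first step is the same level. No data collection or sample size changes.

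The costs are a changed decision rule and the loss of simple matching simultaneous intervals. An ineffective third dose is also rejected more often when the other two work (1.7% to 3.9% at SD 0.50, still under 5%). If the sponsor prefers tests and intervals that agree exactly, the alternative is to keep 0.0167 and report 98.33% intervals for the three contrasts. These are 22% wider (2.411/1.970 = 1.22; half-width 0.22 against 0.18 mmol/L at SD 0.50).
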